1.7 Study Design

There is compelling biological and clinical rationale for including exercise in the clinical management of men with MCRPC. We propose that psychosocial support plus exercise will increase OS compared to psychosocial support alone. This will be a phase III RCT of high intensity aerobic and resistance exercise training among men with MCRPC. The first twelve cycles (1 cycle=28 days) of training will be done under supervision which will include a structured period of tapered supervision to self-managed exercise; the training program will be self-maintained with text messages and in-person sessions to support self-maintenance for an additional 12 cycles.

Figure 2. Study Design

1 cycle=28 days

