5.2 Exercise Laboratory Measurements (SOM: [Appendices 14-16](#))

The following exercise assessments will be completed in both the intervention and the control group at screening/baseline (see note) and within 7 days on or after day 1 of Cycle 6, 12, 18 and 24, subject to location of bone metastases.

NOTE: The first cardiopulmonary exercise test will be completed during the screening period to ensure eligibility. The results of the screening measure will be used as the baseline result. Subsequent assessments will be completed over two days (Day 1: Cardiopulmonary exercise test; Day 2: 400m Walk test, 1RM test) at least 48 hours apart for Cycle 6 and Cycle 12, and over 1 day for Cycles 18 and 24.

1. Cardiopulmonary Exercise Test (During screening 2-14 days prior to Cycle 0, and within 7 days on or after Day 1, Cycle 6 and 12)
2. 400m Walk Test (completed on Cycle 0, and within 7 days on or after Day 1, Cycle 6, 12, 18, and 24)
3. Strength assessment (completed on Cycle 0, and within 7 days on/after Day 1, Cycle 6, 12, 18, and 24)
 - a. 1RM Chest Press
 - b. 1RM Leg Press
 - c. 1RM Seated Row
 - d. 1RM Leg Extension

Aerobic fitness and muscle strength will be monitored in the exercise intervention group only to inform exercise prescription and progression throughout the supervised exercise program. The following exercise monitoring assessments will be completed, subject to location of bone metastases.

1. Strength assessment (completed within 7 days on or after Day 1 of Cycle 9)
 - a. 1RM Chest Press
 - b. 1RM Leg Press
 - c. 1RM Seated Row
 - d. 1RM Leg Extension
2. Constant Load Exercise Test (completed within 7 days on or after Day 1 of Cycle 0-24/Off-Study Visit)

Full details of all assessments can be found in SOM: [Appendix 13: Exercise Physiologist Manual #1 – Exercise Testing Instructions](#).

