6.1.4 Transition to self-managed exercise program

After 9 cycles, participants will be transitioned to self-management across a 3 cycle period. The number of supervised exercise classes will be tapered from 2 classes/week during cycles 1-8, to 1 supervised training session during cycles 9, 10 and 11. Aerobic exercise will be tapered first followed by resistance training classes. Throughout the supervised intervention period (Cycles 0-11), the intervention arm will complete the Constant Load Exercise test (within 7 days on or after Day 1 of Cycles 0-11) and 1RM strength testing (within 7 days on or after Day 1 of Cycle 9) to monitor progression and adherence to the prescribed protocol and inform continued progression of exercise prescription. Participants will be provided with heart rate monitors to wear for the duration of the supervised intervention (cycles 0-11) to monitor aerobic exercise prescription. The specifics of the self-managed program can be highly variable so long as across a given one to three cycle period the participant averages the equivalent of 75 minutes of vigorous aerobic exercise and two resistance training sessions each week. The key criteria for adherence and compliance will be that the participant meets the target aerobic and resistance training as per their individual exercise prescription. Participants will be reassessed within 7 days on or after Day 1, Cycle 12, following which they will be instructed to continue with self-managed exercise until Day 1, Cycle 24, disease progression, or patient mortality, whichever occurs first. The intervention period will cease at Cycle 24.

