2x week self-managed; 1x week supervised Cycles 9-11	The behavioural support will focus on: 
 ○ Identifying and overcoming barriers to exercise ○ Finding areas/ways/places to exercise ○ Self-monitoring ○ Goal setting ○ Time management ○ Lapsing/Relapsing/Collapsing ○ Gaining confidence ○ Perceived independence ○ Making exercise fun ○ Perceived competence ○ Staying motivated ○ Maintaining/enhancing self-efficacy ○ Securing social support 
 ➤ 3x per week pt. would get a text message emphasising 2 of the topics above “signed” by the exercise specialist – each week would be a different pair working “down” off the list
Totally self-managed; 1x supervised session approximately every four weeks Cycles ≥ 12	The behavioural support will focus on a ‘kitchen sink’ approach: 
 ○ Identifying and overcoming barriers to exercise ○ Finding areas/ways/places to exercise ○ Self-monitoring ○ Goal setting ○ Time management ○ Lapsing/Relapsing/Collapsing ○ Gaining confidence ○ Perceived independence ○ Making exercise fun ○ Perceived competence

- Staying motivated
- Maintaining/enhancing self-efficacy
- Securing social support
- 5x per week pt. would get a text message emphasising 2 of the topics above “signed” by the exercise specialist – each week would be a different pair working “down” off the list.

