9.0 OFF-TREATMENT

Subjects will remain on treatment until the Month 24 Off Study visit; however, a patient may be discontinued from study intervention at any time if the patient, the Investigator, or the DSMB feels that it is not in the patient's best interest to continue on study. If a patient must be discontinued, this will not result in automatic withdrawal of the patient from the study.

The following is a list of possible reasons for early discontinuation of study interventions:

- An adverse event that cannot be adequately managed with intervention modifications
- Protocol violation requiring discontinuation of study intervention
- Lost to follow-up
- Patient withdrawal of consent
- DSMB request for early termination of study
- Progression is NOT a reason for study termination

All patients discontinuing study interventions will complete an Off Study visit (if able), and enter into the follow-up period.

If a patient is lost to follow-up, every reasonable effort must be made by the study site personnel to contact the patient and determine the reason for discontinuation/withdrawal. The measures taken to contact the patient must be documented. When a subject withdraws before completing the study, the reason for withdrawal is to be documented in the CRF and in the source document. Subjects who withdraw will not be replaced.

Note: PROGRESSION: Every effort should be made to keep patients who progress on study for the duration of the trial period.

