14.2 Withdrawal of participants

Participants are free to withdraw from the trial at any stage without providing a reason and without consequence. This information will be stated in the participant information leaflet. Participants can inform the research team at their local site of their decision to withdraw. If a participant withdraws from the study, any data collected on him up to that point in the study will go forward for study analysis. This information will be stated in the participant information leaflet. If a participant withdraws from the intervention, but provides consent to complete subsequent follow-up measurements he will continue to attend study assessments and data will be used for intention-to-treat analysis. If a patient chooses to withdraw prior to cycle 24, we will ask for an Off-Study research blood draw if research bloods were not taken within the last 56 days. Reasons for stopping the intervention will be recorded and reported.

Reason	Comment
Self-withdrawal (withdrawal of consent)	Patients may permanently discontinue study treatment and withdraw from the study anytime for any reason. Following study intervention discontinuation, patients will have protocol-required safety and long-term follow-up assessments unless the patient specifically declines further follow-up.
Adverse event or intercurrent illness	Any intolerable adverse event (associated or not associated with the study intervention) that cannot be ameliorated by the use of adequate medical intervention or that in the opinion of the site investigator would lead to undue risk if study treatment were continued.
Gross noncompliance with protocol (violation)	The investigator may request permanent discontinuation of study treatment in the event of a major protocol deviation, lack of cooperation, or complete noncompliance. Outcome and follow-up data will still be requested unless the participant specifically declines further follow-up.
Loss to follow up	Reasonable effort should be made to contact any patient lost to follow-up during the course of the study in order to complete study-related assessments, and record outstanding data.

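### Section 6.1.4 ends Arm A self-managed exercise (Cycles 12 to 24) at disease progression, in conflict with section 9.0, which keeps subjects on treatment to Month 24 and does not accept progression as a reason to discontinue

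*Combined protocol and SAP*

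**What the plan says.** Section 6.1.4 governs the second half of the Arm A programme. Men are reassessed at Cycle 12 and then told to carry on with self-managed exercise "until Day 1, Cycle 24, disease progression, or patient mortality, whichever occurs first". Progression is thus one of three events that end the instruction, and no clinical judgement is attached to it. The section does not define progression or refer to another section for it.

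Section 9.0 opens differently: "Subjects will remain on treatment until the Month 24 Off Study visit". It allows a patient, the investigator or the monitoring board to stop the intervention in the patient's interest. It then gives a list introduced by "The following is a list of possible reasons for early discontinuation of study interventions". The list names unmanageable adverse events, protocol violations, loss to follow-up, withdrawal of consent and a board request. Its last entry reads "Progression is NOT a reason for study termination". A closing note asks for every effort to keep men who progress on study.

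Other sections describe the same period without mentioning progression:
- Section 1.7 has training "self-maintained with text messages and in-person sessions to support self-maintenance for an additional 12 cycles".
- Table 4 in 6.1.8 describes the phase from Cycle 12 as "Totally self-managed; 1x supervised session approximately every four weeks".
- Section 5.2 schedules for Arm A the "Constant Load Exercise Test (completed within 7 days on or after Day 1 of Cycle 0-24/Off-Study Visit".
- Section 14.2 states "Reasons for stopping the intervention will be recorded and reported", and its table of reasons does not include progression.

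**The concern.** Sections 6.1.4 and 9.0 are both current instructions on the same question, whether a man in Arm A who progresses in the second year keeps exercising, and they give different answers. The primary analysis is an intention-to-treat comparison of overall survival. Followed literally, 6.1.4 takes the tested exercise away from men in one arm when they progress. If sites choose differently, the second-year dose varies by site for a reason unrelated to the patient. It also becomes unclear whether the trial estimates the effect of exercise up to progression or through it.

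The breadth of progression adds to this. Under section 11.1 it covers new bone lesions, growth on CT or MRI, a symptomatic skeletal event, or development of an indication for a new therapy for the disease. If 6.1.4 is read with that definition, a man able to train could be told to stop because his drug treatment changed.

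**Working it through.** **Text comparison**

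| Question | Section 6.1.4 | Section 9.0 |
|---|---|---|
| How long does the intervention last? | To Cycle 24, progression or death, whichever is first | To the Month 24 visit |
| Does progression stop it? | Yes, automatically | Negated within the list of reasons to discontinue interventions |
| Is there room for judgement? | None stated | Yes, case by case |

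Month 24 and Cycle 24 denote the same Off-Study visit (5.5.10), so the labels are not the source of the conflict. The 6.1.4 sentence starts after Cycle 12 and sets no progression-free condition for entering the self-managed phase. I therefore read it as covering progression during Cycles 12 to 24 only.

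**Size (illustration)**

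The plan states no figure to reproduce.

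Inputs:
- Window: Cycle 12 Day 1 is 12 × 28 = 336 days, a = 11.04 months. Cycle 24 Day 1 is 672 days, b = 22.08 months.
- Overall survival: exponential, control median M = 33.5 months (12.2), or 33.5/0.78 = 42.9 months at the design hazard ratio.
- Time to progression: exponential with median m = 12, 20 or 36 months. These medians are assumed.
- Progression and death are taken as independent, and every man who progresses in the window is taken to stop completely. Both are assumptions.
- Arm A: 866/2 = 433 men.

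Formulas, with S_OS(t) = 0.5^(t/M), S_p(t) = 0.5^(t/m), f_p the density of time to progression, and integrals from a to b:
- Self-managed cycles alive under 9.0 = 12/(b − a) × ∫S_OS
- Share progressing while alive in the window = ∫f_p × S_OS
- Cycles lost under 6.1.4 = 12/(b − a) × ∫S_OS × [S_p(a) − S_p(t)]

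Example with M = 33.5 and m = 20: ∫S_OS = 7.854 and ∫S_OS × S_p = 4.484.
- Cycles alive = 12/11.04 × 7.854 = 8.54.
- Share progressing = (ln 2/20) × 4.484 = 15.5%.
- S_p(a) = 0.682, so cycles lost = 12/11.04 × (0.682 × 7.854 − 4.484) = 0.95.

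| M | m | Progress alive in window | Men of 433 | Cycles alive | Cycles lost | Share lost |
|---|---|---|---|---|---|---|
| 33.5 | 12 | 17.9% | 78 | 8.54 | 1.14 | 13% |
| 33.5 | 20 | 15.5% | 67 | 8.54 | 0.95 | 11% |
| 33.5 | 36 | 11.1% | 48 | 8.54 | 0.66 | 8% |
| 42.9 | 12 | 19.3% | 83 | 9.20 | 1.23 | 13% |
| 42.9 | 20 | 16.7% | 72 | 9.20 | 1.03 | 11% |
| 42.9 | 36 | 11.9% | 52 | 9.20 | 0.72 | 8% |

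Dividing cycles lost by the share progressing gives 6.0 to 6.4 cycles for each man who progresses in the window. Against all 24 planned cycles, the average loss is 0.66/24 to 1.23/24, about 3% to 5%.

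**The case against.** The best defence is that 9.0 speaks of study termination and of keeping men on study. It also separates stopping the intervention from leaving the study. On that reading a man could stop exercise at progression and stay in follow-up, and the two sections would agree. This explains the wording of the progression entry. It does not explain why that entry sits in a list about discontinuing interventions, or why the opening sentence keeps subjects on treatment to Month 24 with no exception for progression. The list is of possible reasons and 9.0 permits discretionary stopping, but neither amounts to an automatic stop.

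Several objections stand and limit the point:
- A reader might infer that 1.7, Table 4, 5.2 and 14.2 also contradict 6.1.4. They do not. The first three are planned schedules, equally silent on adverse events and withdrawal, which do stop exercise. The 14.2 table concerns withdrawal and is not stated to be exhaustive. Only 9.0 truly competes.
- A reader might cite the absence of new therapy from Table 5 as evidence against the progression stop. Table 5 lists acute signs for stopping a test or session and says nothing about ending the programme.
- 6.1.4 ends an instruction and does not prohibit exercise. Counting every progressor as stopping completely therefore gives an upper bound for the window. By then the 88 supervised sessions planned for Year 1 (6.1) should be complete.
- The Cycles 12 to 24 limit is a reading. The text does not say what happens to men who progressed earlier. If they too were told to stop, the figures would be larger.
- The operations manual, to which section 6 refers for the Arm A programme, may settle the matter for sites. It is not among the documents.

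**Conclusion.** The conflict holds, chiefly between 6.1.4 and the opening sentence and discontinuation list of 9.0. Literal use of 6.1.4 would withdraw second-year exercise from men who progress. How many is unknown. The illustrated upper bound of 11% to 19% of Arm A, and 8% to 13% of self-managed cycles alive, depends on the assumed progression medians, independence of progression and death, and complete stopping.

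A reader might infer that the survival comparison is biased or that power has been lost. The documents do not support this. Men are analysed as randomised whether or not exercise stops, and the intention-to-treat set, sample size, supervised year and 80% per-protocol rule are unaffected. No effect on the hazard ratio can be derived from the plan. Nor do the documents show which section sites follow, so it cannot be said that exercise is in fact being stopped. The amendment should be made because it is cheap and concerns delivery of the tested intervention. Confidence is high that the wording conflicts and low about the size of any effect.

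**What to change.** Remove 'disease progression' from the stop rule in 6.1.4, so that only Day 1 of Cycle 24 and death end self-managed exercise. State that men who progress continue unless discontinued under 9.0.

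The deletion should not be made alone. Section 13.1.1 says that progression assessed by lesion measurement is not reported as an adverse event unless fatal. New asymptomatic bone lesions would therefore not trigger the return-to-exercise process in 6.1.7, and routine clearance under 5.5.9 comes only every six cycles. Add that, at progression, the treating physician and the ECC re-review the prescription under 6.1.3 and Table 3, in particular for new bone lesions, before training resumes. Do not cite Table 5 as a ground for ending the programme. Notify sites.

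The cost is a wording amendment, a site notice and a brief review at progression, using consultation that 6.1.3 already requires.

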6.1.5 Missed sessions

Missed sessions should be rescheduled within the same week, if possible, while allowing at least 48 hours between resistance exercise sessions. Three sessions total (supervised and self-managed sessions) are recommended per week; however up to 3 sessions can be recovered (added) per week if missed in other weeks, totalling a maximum of 6 sessions within one week. The total number of supervised sessions and self-managed exercise sessions should remain the same as originally planned for in Year 1. When recovering missed sessions in a given week, we strongly advise to add 1 additional session per week (totalling 4 exercise sessions) where feasible, so as to not overwhelm the patient. Supervised sessions can occur during the week, which might require self-managed sessions to be moved to a mid-week and/or weekend day to facilitate recovering missed sessions. In the event that more than one missed session is being recovered in a given week, you may reduce volume/intensity in collaboration with the exercise coordination centre to prevent patient overreach. Incorporating additional exercises into a scheduled session to make up missed exercises is allowed and should be discussed with the ECC.

Exacerbation of symptoms such as fatigue should not result in missed sessions, as each training session can be adjusted (auto-regulated) to the patient's current condition on that day. Attendance will be defined as the number of in-person exercise sessions attended divided by the total number of planned supervised sessions. Exercise physiologists/trainers, leading the intervention will guide modification of the prescribed protocol based on the participant's capacity and perception of effort at the time of presentation to each exercise session in line with the principles of auto-regulated training outlined above. The number of missed sessions per participant and the reasons for missing sessions must be recorded and reported. If a participant misses an exercise session, they will be contacted by the research team to determine the reason and to reschedule the session. Every effort must be made by the research team to reschedule missed sessions or add extra exercise to current sessions in order to meet exercise targets.

Patients are permitted to take holidays however must commit to self-management of exercise during this period. During pre-planned or spontaneous holidays for patients (while on-trial), and/or due to unforeseen circumstances precluding attendance to a supervised session (such as an illness to spouse, or conflicting medical appointment), patients may complete a self-managed session under the strict guidance and overview of the site's research coordinator and exercise physiologist (to be recorded). If this occurs, a self-managed session replacing a supervised session in this way must be recorded in REDCap. If no session is performed to recover the missed session (without any adverse event, or other justifiable reason), this will be recorded in REDCap. During holidays, if patients do not have access to exercise facilities or equivalent items of use, these can be recovered during subsequent weeks within the Year it occurs (as is the definition of autoregulation; to ensure the overall program is upheld). This will be monitored by the Study and Exercise Coordination Centres during routine monitoring visits.

6.1.6 Trainer/Exercise Physiologists Training Program

Exercise professionals must complete an online training course (6 education modules and 3 protocol modules) on the protocol's exercise assessment and intervention methods. Trainers will view tutorials on the standard operating procedures, videos of specific tests/exercises, and guidelines on modifying assessments/exercises based on the patient's physical condition. A website with a discussion forum for trainers to submit queries and to discuss issues pertaining to the intervention will be maintained throughout the intervention period. This training program will include site requirements and ECC expectations in site monitoring of patients and ensuring regular and accurate entry into Physitrack.

6.1.7 Return to Exercise Training Following an Adverse Event

Return to exercise following reporting of an adverse event which requires updated physician clearance will be discussed on a case by case basis with the Exercise Coordinating Centre. Where physician clearance to return to exercise is deemed necessary, the participant will only be allowed to return to exercise training when physician clearance is provided in writing. The exercise physiologist/therapist supervising the exercise program will modify the program accordingly at re-introduction. A template form for physician approval for a patient to return to exercise is provided in SOM: [Appendix 9](#). If no physician clearance is deemed necessary the participant can return to training upon clearance from the exercise physiologist/therapist.

6.1.8 Behavioural Support Program (Intervention Arm Only)

Participants will be asked to complete at least one unsupervised exercise session per week (hereafter referred to as self-managed exercise) starting in Week 5 (Cycle 1). The more self-managed exercise the participants are asked to engage in, the more behavioural support will be provided. The behavioural support will be provided utilizing text messages rooted in constructs/strategies from Social Cognitive Theory (SCT) and the Theory of Planned Behaviour (TPB). The overarching focus of the behavioural support will be to increase/enhance perceived control in task-specific exercises and overcoming individual barriers to exercise. The behavioural support provided will be encompassing, consistently delivered, and provided to each participant throughout the program. There will be four 'levels' of behavioural support ([Table 4](#)):

1. [3x/week supervised \(cycle 0\)](#)

2. 1x/week self-managed; 2x/week supervised (cycles 1-8)
3. 2x/week self-managed; 1x/week supervised (cycles 9-11)
4. Totally self-managed; 1x/cycle supervised (cycles ≥ 12)

Table 4. Guidelines for Level of Behavioural Support

Level of Self-Management	Behavioural Support Components
No self-management 3x week supervised Cycles 0	The behavioural support will focus on: 
 ○ Perceived competence ○ Identifying and overcoming barriers to exercise ○ Goal setting ○ Enhancing self-efficacy 
 ➤ 1x per week pt. would get a text message/e-mail emphasising one of the topics above “signed” by the exercise specialist. Each week would be a different message working “down” off the list
1x week self-managed; 2x week supervised Cycles 1-8	The behavioural support will focus on: 
 ○ Perceived independence ○ Securing social support ○ Maintaining/enhancing self-efficacy ○ Identifying and overcoming barriers to exercise ○ Self-monitoring ○ Goal setting 
 ➤ 2x per week pt. would get a text message emphasising 2 of the topics above “signed” by the exercise specialist – each week would be a different pair working “down” off the list.
2x week self-managed; 1x week supervised Cycles 9-11	The behavioural support will focus on: 
 ○ Identifying and overcoming barriers to exercise ○ Finding areas/ways/places to exercise ○ Self-monitoring ○ Goal setting ○ Time management ○ Lapsing/Relapsing/Collapsing ○ Gaining confidence ○ Perceived independence ○ Making exercise fun ○ Perceived competence ○ Staying motivated ○ Maintaining/enhancing self-efficacy ○ Securing social support 
 ➤ 3x per week pt. would get a text message emphasising 2 of the topics above “signed” by the exercise specialist – each week would be a different pair working “down” off the list
Totally self-managed; 1x supervised session approximately every four weeks Cycles ≥ 12	The behavioural support will focus on a ‘kitchen sink’ approach: 
 ○ Identifying and overcoming barriers to exercise ○ Finding areas/ways/places to exercise ○ Self-monitoring ○ Goal setting ○ Time management ○ Lapsing/Relapsing/Collapsing ○ Gaining confidence ○ Perceived independence ○ Making exercise fun ○ Perceived competence

- Staying motivated
- Maintaining/enhancing self-efficacy
- Securing social support
- 5x per week pt. would get a text message emphasising 2 of the topics above “signed” by the exercise specialist – each week would be a different pair working “down” off the list.

